- 1.4. If a survey study, specify the estimated amount of time that subjects will need to complete the questionnaires/tools. **Approximately 40-60 minutes**
- 1.5. If a blood draw, specify the amount of blood to be drawn in milliliters and in teaspoonfuls or tablespoonfuls and specify how often and where the blood will be drawn. **N/A**

2. **Data Collection** (Include all questionnaires and survey tools with the submission.)
 - 2.1. Provide
 - 2.1.1. the mode of data collection, e.g. telephone, in-person, questionnaire, interviews, **All research assessment, questionnaire data (unless in cases where the CG prefers to complete a follow-up research assessment packet at home) and data collected over the course of care management will be collected via telephone. Medical and pharmaceutical claims data will be collected via VINCI (please see detail below). Data will be coded and identifiable.**
 - 2.1.2. the precise plan for how data is to be collected or acquired

Research Assessment and Care Management Data Collection Procedures: The vast

majority of research assessment and care management data will be collected by telephone and entered electronically on a password-protected website run by the CMCVAMC's Data Management Unit (DMU) or on the Research Electronic Data Capture website (REDCap). The DMU is a closed data entry system that has been designed so that only the responsible data entry person and the DMU supervisor can enter and/or edit data. The PIs or research staff from both sites will be able to access and request the data at any point during the study so that audits of the study's current data input can be conducted and the data's integrity assessed. Data will be stored on the CMCVAMC's Data Management Unit or REDCap for the duration of data collection. REDCap (Research Electronic Data Capture) is a web-based application for managing data acquisition during clinical research. REDCap is supported by the VA Information Resource Center and is maintained within the VA firewall so that it is only accessible on the VA intranet. REDCap will be used in this study for data entry. For participants completing the interview via phone, a blank copy of the assessment will be sent in advance of the scheduled assessment calls to help facilitate the interview. We will ask each respondent whether they are in a safe, private setting and if they are assured that their responses are not being monitored in order to ensure candid responding. Research assessment data also will be collected using hard copy, paper versions of the data forms should the CG prefer to complete the research assessment on their own. The paper versions will be created using Cardiff Teleform software and mailed to CGs along with a stamped return envelope.

Medical and Pharmaceutical Claims Data Collection Procedures: We will work with VINCI in order to expedite chart extraction of clinical data including VA and, where possible, non-VA medical/pharmaceutical, encounter, and fee information, as well as mortality status of the care recipients. When estimating non-VA utilization/cost of care (e.g., community nursing home care, home-based care, etc.), we plan to follow HERC's guidebook which provides detailed documentation and suggestions for extracting and analyzing data on cost and procedures.⁶ The database will also include a "time window" variable spanning one year prior to and one year following the 3 month research assessment. Specifically, we will ask for stop codes, ICD-9/DSM-IV codes, CPT codes, and pharmacy fill dates/days supply. We also will separately consider high cost health care utilization (e.g., ER visits, walk-in clinic visits, inpatient stays) and utilization of scheduled primary and specialty care services. Extracting clinical patient record data electronically will greatly improve validity and reduce respondent burden.

- 2.1.3. exact location where data will be collected, **by phone, either at the CMCVAMC MIRECC and CHERP or VAWNYHS Center for Integrated Healthcare; by hard copy, in the CG's home (completion of self-report assessments)**
- 2.1.4. exact location where data entry will take place. **CMCVAMC MIRECC, 2nd Floor, Suite B228; CMCVAMC CHERP, Annex, 2nd Floor, Suite 202, VAWNYHS Center for Integrated Healthcare**
- 2.1.5. the "title" of individual(s) collecting the data and analyzing the data, e.g. principal investigator, research coordinator. **Research Assistant, Project Coordinator, and Care Managers will all collect and enter data. PI and Biostatisticians will manage and analyze the data.**

2.2. Provide a time line for each aspect of the study.

Figure 2. Gantt Chart for Proposed Project Timeline

Project Year	One					Two		Three		Four	
Project Month	1-2	3	4-5	6	7-12	1-11	12	1-11	12	1-10	11-12
Calendar Year	2015					2016		2017		2018	
Calendar Month	Jan-Feb	Mar	Apr-May	Jun	Jul-Dec	Jan-Nov	Dec	Jan-Nov	Dec	Jan-Oct	Nov-Dec
PREPARATORY PHASE											
Train preexisting BTC/MIRECC RA/CM											
Hire & train Care Managers, Project Coordinator, and RA(s)											
Receive Final IRB/R&D Approval											
Finalize DMU forms and form development; prepare TEP manuals and study material for distribution to participants											
Enroll project with VINCI and specify data to be extracted											
Create randomization and tracking databases (the latter will be managed via VINCI)											
Meet with BHL and BTS staff to review study objectives; distribute study fliers to clinical staff											
Hold virtual team meetings											
SAMPLING, RECRUITMENT, and DATA COLLECTION PHASE											
Extract list of eligible Veterans from VINCI (ongoing, periodic activity)											
Commerce recruitment, rolling enrollment, BL assessments, care management calls, and TEP groups (for those randomized to TEP group delivery)											
Begin and continue follow-up research assessments											
Recruit last wave of caregivers and initiate care management/TEP (3 month duration) for last wave of CGs randomized to active intervention arms											
Extract VINCI clinical, encounter, utilization & cost data (ongoing, periodic activity)											
DATA ANALYSIS, DISSEMINATION, and IMPLEMENTATION PHASE											
Data entry and cleaning (periodic, ongoing activity)											
Merge randomization assignment, DMU, and VINCI databases (periodic, ongoing activity)											
Begin and continue data analyses (interim and final)											
Begin and continue dissemination efforts											

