B. Baseline and 3, 6, and 12 month Follow-up Procedures (all participants, regardless of randomization): Once the CG is recruited, screened, and randomized (greater detail on recruitment, screening and randomization provided below), the Research Assistant will contact the CG for the baseline research assessment (please refer to Appendix I for list of assessments and related citations). This assessment will include a battery of standardized, well validated questionnaires regarding CRs/CGs' sociodemographic characteristics, CRs' dementia-related symptoms and associated CG distress and burden, CGs' mental and physical functioning, CGs' social network structure and function, and CRs' psychiatric symptoms, comorbid medical conditions, and physical functioning. All research assessments will be re-administered at 3, 6, and 12 month follow-up. At the beginning of each research assessment, RAs will remind participants that they are not aware of their group assignment and will ask that participants not disclose which of the study arms they participated in. Data on CRs' medication use and inpatient/outpatient medical service use will be extracted from the CRs' clinical record. Data will be coded and identifiable.

C. Intervention Procedures:

i. Care Management: CGs assigned to both active intervention arms will receive care management services. Care management will involve regular contact between CGs, PCPs, and the care manager. The care manager, who will be a nurse or licensed clinical social worker with at least 2 years of experience in clinical/research settings, will monitor CRs' symptoms, provide psychoeducation and support to CGs, influence adherence to VA concordant care guidelines by providing timely and tailored information to PCPs, and collaboratively make appropriate care decisions and service referrals. The care managers will be supervised and meet weekly to review active cases and discuss individual action plans either in person or virtually with a clinical psychologist (Drs. [name] or [name]) or geriatric psychiatrist ([name]). This supervision process has been successfully used in our past collaborations.

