Following the baseline assessment, the care manager will contact CGs a minimum of 3-4 times over the course of 3 months to complete clinical/needs assessments. *All CGs randomized to the two intervention arms will receive these individual care manager contacts.* The number of visits/calls will be determined based on clinical judgment and perceived CG need. During these visits/calls, the care manager will assess CRs' and CGs' general service use and needs. Questions about CRs' dementia-related behavioral and memory issues and CGs' mood also will be asked. Corresponding care plan(s) will be developed. CGs will be contacted specifically at approximately 2, 5, and 9 weeks after the baseline assessment for brief follow-up phone calls designed to monitor, via CG report, patients' medication adherence, side effects, and symptoms. If appropriate, after the visit/call (including the medication monitoring calls), a report summarizing patient and CG outcomes will be generated and sent to each CG along with educational materials regarding specific reported symptoms. The care manager will help coordinate connection to VA and community programs, if needed. Progress reports also will be generated, where appropriate, for patients' PCPs following interviews/contacts to help in treatment planning and to alert clinicians of special issues. The care manager will personally contact PCPs to discuss cases in which CRs are not improving and/or experiencing significant symptoms or side effects (either via phone, encrypted email, fax, or a research note in CPRS). They also may contact the PCP throughout the study regarding the CG's status, particularly in regards to caregiver distress and burden. Based on the severity of symptoms and medical service needs reported, the care manager also may make recommendations and help coordinate scheduling in primary and specialty care. For tracking and process evaluation purposes, the care manager will keep log sheets and document each contact with CGs, community/VA service agencies, and PCPs/providers.

ii. Telehealth Education Program (TEP): The second major component of the intervention is the TEP. The program includes both a CG workbook and care manager manual. All CGs will be sent the entire workbook, which includes education material and summarizes and outlines homework for each of the modules. The delivery of TEP will vary depending on randomization group as follows:

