- a) Individual Delivered TEP Arm:** Based on evaluation of the baseline interview, the CG and care manager will work together to determine which of the modules are most appropriate for the CG. In addition to two mandatory modules that cover the stages of dementia and provide a brief introduction to problem solving techniques, action plan development, and coping skills, CGs can select from a menu of additional modules covering various content areas evaluated during the course of the monthly assessments (e.g., communication skills, behavioral management techniques, stress management and coping skills, long-term planning, etc.). Each individual TEP session will begin with reviewing education related to the selected module. The remainder of each session will involve coaching the CG on emotion-focused and problem-focused coping strategies. The care manager will also discuss problem solving with the CG to reinforce the action plan and the educational component of the intervention. Each session will be delivered over the telephone and will last 40 minutes-1 hour. Sessions will occur approximately every other week, depending upon the availability and preference of the CG. The number of TEP contacts will depend on the number of topics chosen and covered.
- b) Group Delivered TEP Arm:** CGs assigned to this arm will be asked to participate in all TEP modules in a group format. Each call will take up to 1.5 hours. Each group will be comprised of 5-8 CGs who will call into a VANTS teleconference line at a pre-specified time. The content of the calls will mirror those in the individual TEP delivered program. As with the individual

TEP delivered program, each session will begin with reviewing a different education topic and the remainder of the call will involve reviewing weekly action plans, discussion of emotion and problem focused coping strategies, and skills training. This arm, however, will include the added component of peer group support. CGs will be given the option of sharing their contact information with one another. CGs will be asked to complete their workbooks prior to the next session.

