In order to monitor the quality of the individual and group care management/TEP sessions and care managers' fidelity to the model, all individual and group sessions will be audiotaped using a digital recorder. 20% of the sessions will be randomly selected by the PI using a random number generator for fidelity purposes. These digital files will be uploaded onto a shared study folder that will reside on the VISN 4 MIRECC server under password protection and made available only to key personnel at both sites. Audio recordings will be encrypted and password protected and will only be used for supervision purposes.

D. Usual Care Procedures: After the initial baseline research assessment described above, participants randomized to UC will be sent general material about VA and community resources for patients with dementia and their CGs. CGs will receive brochures entitled: Rewards of Caregiving; Caring for the Caregiver; A Checklist for New Caregivers; 5 Tips to Avoid Caregiver Burnout; 50 things Every Caregiver Should Know; Balancing Caregiving, Family, and Work; and, Long Distance Caregiving. With the exception of this material, individuals in this group will receive UC and will be contacted again at 3, 6, and 12 months for follow-up research assessments. CGs in the UC group will be free to seek medical, psychological, social support, and social services that are available through VAMCs or any other non-VA/community source.

- 1.2. Explain if and how the follow-up of subjects will occur. **Follow-up CG research assessments will be conducted at 3, 6, and 12 months post-baseline. CG assessments will be conducted by phone or, if the CG prefers, packets will be mailed to the CG along with stamped, return envelopes. CRs' medical charts will be reviewed for a period of up to one year following the 3-month CG assessment.**
- 1.3. Describe where, how and who will be conducting study procedures. **Randomization group will be assigned by the PI, Research Coordinator, or Biostatistician. Screening, research assessments, and chart reviews will be conducted by the Research Assistants. Care management will be provided by Care Managers. Supervision will be provided by Drs. [name], [name], and [name]. All procedures will be conducted at either the CMCVAMC MIRECC or CHERP or VAWNYHS Center for Integrated Healthcare (except in the case where the CG prefers to have the assessment packets mailed to them).**

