Patients referred to study staff through these mechanisms will receive a letter stating that their provider has identified them as someone who might be appropriate for a new program designed to help Veterans with memory problems and their CGs. Within one week of receiving this letter, Veterans and CGs will be called by the Research Coordinator/research assistant to assess interest in participation. We will call the contact number in the Veteran's medical record. If the Veteran answers, we will describe the study and ask for the name and contact information of the family caregiver. The Veterans' identity will be verified by first asking for their full name and the name of their CMCVAMC primary care physician. After telephone discussion of the information in the consent/HIPAA form, and encouraging the asking of questions/concerns, the CG will be asked if s/he gives consent to be enrolled in the study. The Research Coordinator/RA will be using an IRB approved script as well as a checklist to ensure each element of consent is covered. Interested CGs will be mailed a copy of the verbal informed consent form. Non-Veteran caregivers also will receive a Copy of Notice of Privacy Practices, and acknowledgement of its receipt will be noted. Once the consent is fully executed, the Research Coordinator/research assistant will confirm study eligibility by completing the screening assessment. Veteran/CG dyads will be eligible for enrollment if they meet the inclusion/exclusion criteria outlined above. Once eligibility is established, the CG will be randomized to one of the three study arms.

- 8.2. If using a clinic, be specific about who will identify the potential subject and how that information will be transmitted to the research staff. **As described above, clinical staff from primary care will be asked to refer potentially eligible participants to the Research Coordinator. At the completion of the initial BHL/BTC clinical behavioral health assessment, all patients potentially eligible for the study who also have a dementia diagnosis will be informed of the project and asked if they would be interested in being contacted by a Research Coordinator in order to discuss a study for which they might be eligible in participating. BHL/BTC staff will be asked to document in an electronic database (stored on the shared secure, password-protected MIRECC server that will be made available to both sites) the names and phone numbers of patients who agree to further contact.**

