9.6. Will informed consent be obtained from potential subjects prior to determining eligibility?

YES NO N/A

9.6.1. If no, provide justification and a HIPAA Waiver of Individual Authorization for Disclosure of Protected Health Information.

- 9.7. Define when a subject is enrolled into the study, e.g. after the subject signs the informed consent or after randomized to treatment. **Subjects are enrolled in the study after randomization to one of the three treatment arms and completion of the baseline interview**
- 9.8. Describe:
 - 9.8.1. The process when informed consent will be obtained and protecting patients' privacy. **Digital recordings of consent (which were part of the study protocol in the past) will be stored on VA servers behind secure firewalls and maintained in accordance with the medical center policy for records and patient/CG information will be entered onto the study-specific electronic tracking spreadsheet which will be stored on the shared MIRECC secure, password-protected server and made available only to study staff. The electronic ICF data will be kept separate from any coded, de-identified data. Paper copies of a consent checklist with only a recruitment ID will be kept in a binder in a locked filing cabinet in the CHERP suite in the annex.**
 - 9.8.2. Any waiting period between informing the prospective participant and obtaining consent. **There will be a short period of time between contacting the CG via mail and obtaining verbal informed consent.**
 - 9.8.3. Steps taken to minimize the possibility of coercion or undue influence. **Potential participants/representatives/CGs will be made aware of the fact that they do not have to take part in this study, and their refusal to participate will involve no penalty or loss of rights to which they or the Veteran are entitled.**
- 9.9. Provide the language
 - 9.9.1. used by those obtaining consent **English**
 - 9.9.2. understood by the prospective participant or the legally authorized representative **English**
- 9.10. Provide location where informed consent will be obtained. **Research offices of the CMCVAMC CHERP (Annex, Suite 202) or VAWYNS Center for Integrated Healthcare (Bldg 20, 1st floor, Room 128)**

10. **Waiver or Alteration of Informed Consent Requirements/Waiver of Requirement to Obtain Documentation of Informed Consent**
 - 10.1. Are you requesting a waiver or alteration of informed consent? *(Check all that apply)*
 - 10.1.1. No

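### Caregivers are randomized before the self-reported baseline interview, although every arm-specific step with a stated date follows it; randomizing after baseline is a cheap improvement

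*Combined protocol and SAP*

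**What the plan says.** The order is stated consistently. Section N.1.1.B, introducing the baseline assessment, says: "Once the CG is recruited, screened, and randomized (greater detail on recruitment, screening and randomization provided below), the Research Assistant will contact the CG". Section Q.8.1 makes the eligibility screen the only precondition: "Once eligibility is established, the CG will be randomized to one of the three study arms". Section L.2.2 likewise triggers randomization once the entry criteria are met. Section Q.9.7 builds in a gap between the two steps: "Subjects are enrolled in the study after randomization to one of the three treatment arms and completion of the baseline interview".

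The arm-specific steps that carry a date come later:

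- Care management, both active arms (N.1.1.C): "Following the baseline assessment, the care manager will contact CGs a minimum of 3-4 times".
- Individual TEP planning (N.1.1.C): "Based on evaluation of the baseline interview, the CG and care manager will work together" to choose modules.
- Usual-care mailing (N.1.1.D): "After the initial baseline research assessment described above, participants randomized to UC will be sent general material".

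Two steps are not dated relative to baseline: the workbook mailing ("All CGs will be sent the entire workbook, which includes education material") and the first group TEP call.

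On roles, Section N.1.3 says: "Randomization group will be assigned by the PI, Research Coordinator, or Biostatistician". The Research Coordinator also recruits, consents and screens (Q.8.1, Q.9.5.1, Q.9.5.5).

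Section V.4.2 describes the primary models as intent-to-treat, adjusts each for the baseline score of its outcome, tests group by time, and says that mixed models use all available data.

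**The concern.** The baseline battery includes the caregiver's own report of distress, burden and mental functioning, which are the three primary outcomes in V.4.2. A caregiver who already knows the arm may answer differently, and the covariate is then no longer a pre-randomization quantity. The documents neither say nor rule out that the arm is known by then. Section N.1.1.B has the Research Assistant ask participants, at the start of each research assessment, not to reveal their arm. That suggests, without proving, that some may know it at baseline.

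The second issue does not depend on disclosure. A caregiver who is randomized and then lost before the interview is not enrolled under Q.9.7. That person has no baseline covariate, and so drops out of a model that requires one. The plan gives 405 as the number randomized (N.1.1.A) and also as targeted enrollment (Q.1: 235 + 170 = 405). Under the Q.9.7 definition, this allows for nobody in the gap.

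**Working it through.** The plan states no figure on this point, so there is nothing to reproduce. The order of events follows from the sections cited above. What remains is how much it could matter, and that depends on how baseline enters the model. V.4.2 calls it a covariate; V.4.1 bases power on four repeated measures per caregiver, which would make it an outcome row as well.

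**Inputs from the documents:** assessments at 0, 3, 6 and 12 months; within-person correlation 0.75; 405 randomized; 10% drop-out; 360 analysed; detectable effect 0.4 SD (V.4.1). **Assumed:** arm-related baseline shift s = 0.1 SD; 5–10% randomized without a baseline.

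**1. Baseline as an outcome row, linear time in months**

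- Mean time = (0 + 3 + 6 + 12)/4 = 5.25.
- Sum of squares = 27.5625 + 5.0625 + 0.5625 + 45.5625 = 78.75.
- Weight of the baseline row on the 12-month slope = 12 × (0 − 5.25)/78.75 = −0.80.
- Bias in size = 0.8 × s, which is 0.08 SD for s = 0.1.

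With complete data the weight was −0.80 in each of four random intercept and slope variance settings tried. If time is coded as visit number 0–3, the weight is 3 × (0 − 1.5)/5 = −0.90.

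**2. Baseline as a covariate only, outcome rows at 3, 6 and 12 months**

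A constant shift between arms is absorbed by the group term. The average adjusted contrast moves by 0.75 × 0.1 = 0.075 SD, but the group-by-time term, which V.4.2 tests, does not. A simulation with correlation 0.75, s = 0.1, 2,000 per arm and 300 runs gave a group-by-time bias of 0.003 per 12 months (Monte Carlo SE 0.002), so about 0.

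**3. How the two harms combine**

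| Role of baseline | No baseline interview | Slope bias from shift s |
|---|---|---|
| Covariate only | excluded | about 0 |
| Outcome row only | kept | 0.8s |
| Both | excluded | 0.8s |

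**4. Loss of caregivers, with the assumed 5–10% on top of the planned 10% drop-out**

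- Without a baseline: 405 × 0.05 = 20; 405 × 0.10 = 41.
- Remaining: 405 × 0.95 × 0.9 = 346; 405 × 0.90 × 0.9 = 328, against 360 planned.
- Detectable effect: 0.4 × √(360/346) = 0.41; 0.4 × √(360/328) = 0.42.

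**The case against.** The strongest reply is that no harm is demonstrated. Slope bias needs three things: disclosure of the arm before baseline, which no section states; a shift for which there is no figure; and baseline used as an outcome row. Under the covariate-only wording of V.4.2, the tested interaction is essentially unbiased. The sample-size effect is small, and it is zero if the planned 10% drop-out already covers people lost before baseline, which V.4.1 does not exclude. The Research Assistants are described as unaware of the arm, and a four-item burden screen is taken before randomization (Q.2.1.1). A lighter remedy exists: withhold the arm until baseline is done, and state how a missing baseline is handled. Reordering could also delay assembly of telephone groups of 5–8, or make randomization wait for a mailed form.

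Most of this stands as a limit on size, but it does not remove the point. Assessor blinding does not protect the respondent's own answers, and the short screen is no substitute for the full battery. The lighter remedy would protect the baseline answers but would still leave people randomized with no baseline. The group-assembly cost is speculative, since assignment moves past only one interview. N.1.1.A allows research assessments on paper, but N.2.1.1 refers to home packets for follow-up, so a mailed baseline does not appear to be intended.

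**Conclusion.** The point holds as an improvement that should be made, not as a demonstrated error. The order of events is certain; whether it does harm is not. Slope bias would be about 0 or 0.8s according to the role of baseline in the model, and the loss of precision would be slight. Both rest on assumed values of the shift and the loss rate. With baseline taken first, the covariate is independent of allocation whenever the arm is disclosed, and nobody is randomized without having had the interview. It does not guarantee complete data, because participants may decline questions (T.1.2) and follow-up can still be missed. Nor does it settle whether baseline is a covariate, an outcome row or both; V.4.2 should say.

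**What to change.** For caregivers not yet randomized, amend N.1.1.B, Q.8.1 and Q.9.7, and bring L.2.2 into line, so that the order is consent, screen, baseline interview, randomize. In N.1.3, state that the assignment is released only once the baseline is recorded, by someone with no recruiting, consenting or screening role; the Biostatistician is already named there.

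For caregivers already randomized under the present order, report by arm how many have no baseline. Keep those with follow-up data in the intent-to-treat analysis, with V.4.2 stating how (for example, with an imputed baseline). Record which order applied to each caregiver.

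The cost is low but not nil. Some interviews of 40–60 minutes (N.1.4) and $20 payments (R.2.1) will go to caregivers who withdraw before randomization. If 5–10% of those interviewed do so (assumed) and 405 are still randomized:

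- Extra interviews: 405/0.95 − 405 = 21; 405/0.90 − 405 = 45.
- Staff time: 21 × 40 min = 14 hours; 45 × 60 min = 45 hours.
- Payments: 21 × $20 = $420; 45 × $20 = $900.

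The assignment must follow baseline promptly, because N.1.1.C times calls at about 2, 5 and 9 weeks after it. Q.9.5.4 mentions past recordings of consent, so recruitment may already have begun. If it has, the trial will have two baseline procedures, to be recorded and reported.
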